5.5. TRIAL RATIONALE

The primary objective of this trial is to assess the efficacy of once-weekly lonapegsomatropin compared to placebo in adults with GHD. The daily somatropin product arm is included to provide a concurrent assessment of standard of care in this patient population. GHD in adults is associated with central adiposity, diminished lean muscle mass, decreased bone mass, and reduced quality of life ([Melmed 2019](#)), and GH replacement therapy represents standard of care treatment that addresses multiple aspects of the condition ([Ho 2007](#), [Molitch 2011](#), [Japan Endocrine Society 2019](#), [Yuen 2019](#), [Kim 2020](#)). Changes in body composition are therefore an objective and sensitive endpoint that reflects biologic activity of GH and clinical efficacy. In similar placebo-controlled trials reporting trunk percent fat over a six-month period in patients with AGHD, the observed treatment effect for somatropin products has varied from -1.53% to -3.50% ([Norditropin US PI](#), [Saizen US PI](#), [Zomacton US PI](#), [Omnitrope US PI](#) and [Genotropin US PI](#)). Although there is no consensus guideline to suggest a minimally important reduction for trunk percent fat ([Hamdy 2006](#)), a change from baseline in trunk percent fat of 1.9% will be clinically meaningful as it represents a significant reduction in the key visceral adipose compartment that is metabolically important.

In addition to assessing efficacy, a treatment duration of approx. 9 months is considered adequate to assess safety and is supported by the well-characterized safety of daily somatropin products for AGHD and extensive clinical experience for lonapegsomatropin for pediatric GHD at higher doses (approximately 2-6 fold based on weight) than used in AGHD.

To assess long-term safety and efficacy, an open-label extension trial is planned. During the extension trial, all subjects will receive lonapegsomatropin.

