10.2.2.2. Visit Schedule of Daily Somatropin Treatment Arm

1. Visit 1 will be performed on the day of the 1st dose (Week 1, Day 1) and all assessments will be done pre-dose, except for the injection site reaction assessment. The first dose will be given on site.
2. Visit 2 (Week 4) and Visit 3 (Week 8) will be conducted at any day of the week.
3. Visit 4 (Week 12) will be conducted at any day of the week. Subjects will be assigned their fixed dose for the next 26 weeks. This dose may be given on site or at the subject's home.
4. Visit 5 (Week 17, +/- 1 week) and Visit 6 (Week 28, +/- 1 week) will be conducted at any day of the week.
5. Visit 7 (Week 38, + 1 week, end of trial) will be conducted the day after the 26th week (or 27th week) of fixed dosing is completed. For subjects not participating in the extension trial: A phone call will be conducted up to 2 weeks after this visit to assess if ongoing AEs are closed. An ADA and a pregnancy test for females of childbearing potential sample will be collected approximately at least 30 days after the last study drug dose.

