12.1.4. Important Identified Risk Associated with Lonapegsomatropin

There have been reports of hypersensitivity and/or anaphylaxis in clinical trials and the post-marketing setting with patients who have been exposed to lonapegsomatropin with/without previous exposure to growth hormone therapy. The reported events resolved after treatment with corticosteroids, antihistamine and /or epinephrine (see section [Appendix 4](#), Anaphylaxis Precautions).

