18.2. SCHEDULE OF EVENTS

Visit	Screening (-6 to Week 1) ^a	Visit 1 (First dose) (Week 1) ^a	Visit 2 (Titration) (Week 4)	Visit 3 (Titration) (Week 8) ^b	Visit 4 (Titration; Start of maintenance dose) (Week 12)	Visit 5 (Week 17)	Visit 6 (Week 28)	Visit 7 (Week 38 + 4 weeks) Early Term, EoT ^c
Weekly Visit Window	– 2 weeks	NA	–	–	–	+/- 1 week	+/- 1 week	+ 1 week
Once-weekly lonapegsomatropin or placebo visit days:	NA	Pre-dose	4-5 days post-dose (96 – 120 h post-dose +/- 3 h)	4-5 days post-dose (96 – 120 h post- dose +/- 3 h)	4-5 days post-dose (96 – 120 h post- dose +/- 3 h)	pre-dose (144 – 168 h post- dose +/- 3 h)	1-3 days post-dose (24 – 72 h post- dose +/- 3 h)	4-5 days post-dose (96 – 120 h post- dose +/- 3 h)
Daily somatropin product visit days:	NA	Pre-dose	Any day	Any day	Any day	Any day	Any day	End of 26 weeks at target maintenance
Informed consent	×							
Medical history, current and prior medications (≤ 12 months prior ICF), Demography	×							
Concomitant medications and AEs ^c	×	×	×	×	×	×	×	×
Subject Diary review			×	× ^o	×	×	×	×
Weight	×	×	×	× ^o	×	×	×	×
Height	×							
Physical examination and vital signs	×	×	×	× ^o	×	×	×	×
GH stimulation test(s) ^d	×							
ACTH stimulation test ^e	×							
MRI / CT scan ^f	×							× ^f
12-lead ECG	×	×						× (weekly treatment arms)
Fundoscopy ^g	×							×
Fasting required	×	×	×		×	×	×	×
Safety laboratory assessments ^h	×	×	×		×	×	×	×
IGF-1 and IGFBP-3 assessments ⁱ	×	×	×	× ^o	×	×	×	×
Pregnancy test for females of childbearing potential	×	×	×	× ^o	×	×	×	×
Samples for PK assessment ^j	×	×	×	× ^o	×	×	×	×
Samples for antibody assessment ^k	×	×	×		×		×	×
DXA scan ^l	×	× ^l			×			×
Study drug administration training	×		×	× ^o (as needed)	×	×	×	×
Scheduled dose titration ^m			×	×	×			
Injection site reaction assessment	×	×	×	× ^o	×	×	×	×
PRO completion ⁿ	×				×		×	×

^a Randomization happens after screening is complete and subject is confirmed to be eligible, up to approx. 1 week is included between randomization and the first dose to allow for logistics and shipments.

^b Visit 3 may be conducted over the phone.

^c The AE collection period begins with signing of ICF and ends at Visit 7 if the subject continues into extension or 2 weeks after the last dose of the study drug.

^d May be conducted according to local protocols. Historic tests may be accepted. Stimulation test protocols and results are subject to review and approval by the Medical Monitor.

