11.3. VISIT TIME WINDOWS

All post-baseline visits will be mapped to the post-baseline scheduled visit with the closest target study day for each scheduled assessment with exception of DXA data, PRO, PK/PD parameters. If the unscheduled visit is in the middle of two scheduled visits, it will be mapped to the later one.

After mapping, if there is more than one visit in the same window, the visit closer to the target assessment day will be used. If more than one visit has an equal distance to the target day, then the later one will be used; if more than one visit occurs on the same day, the time or the sequence number will be used to select the later record. For listings, all data points (as observed) will be included.

Table 2: Analysis Window

Visit	Week	Target Study Day	Study Day Window
Visit 1 (Pre-dose)/Baseline	Week 1	1	<=1
Visit 2	Week 4	29	2-43
Visit 3	Week 8	57	44-71
Visit 4	Week 12	85	72-102
Visit 5	Week 17	120	103-158
Visit 6	Week 28	197	159-232
Visit 7	Week 38	267	233 - (316 or <= first dose date in the TCH-306 EXT which ever is earlier)
Safety Follow-Up ¹		Date of last dose + 28 days	Date of last dose date + 7 days - Date of last dose + 49 days

Study day is calculated with respect to the date of the first dose of trial drug (Study Day 1). Safety Follow Up visit will be included for ADA analysis collected at Safety follow up visit¹.

For the analysis of primary, secondary, tertiary endpoints and exploratory endpoints [REDACTED] assessed by DXA, following study day window will be used:

- Week 12, analysis will be performed based on the assessments performed at the scheduled visit.
- Week 38: Target Day of 267 and Study Day window from 240 - (295 or last assessment taken on or prior to the first dose date in the TCH-306 EXT, whichever is earlier)

After mapping, if there is more than one DXA assessment in the same window, the visit closer to the target assessment day will be used. If more than one DXA assessment with an equal distance to the target day, then the later one will be used in the analysis.

For the analysis of PRO [REDACTED] and PK/PD parameters including IGF-1 and IGFBP-3, analysis will be performed based on the assessments performed at the scheduled visit. For listings, all data points (as observed) will be included.

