12.12.1. Adverse Events

Adverse events will be coded by system organ class (SOC) and preferred term (PT) using the Medical Dictionary for Regulatory Activities (MedDRA) Version 26.0 (the most current March version of the dictionary).

An AE (classified by preferred term) will be considered a treatment emergent adverse event (TEAE) if it occurred on or after the first dose of investigational product and was not present prior to the first dose, or it was present at the first dose but increased in severity during the trial through 14 days after the last dose of treatment on the main period or the date of first dose on the extension period whichever occurs first.

- Summary of TEAEs by treatment
- TEAEs by treatment, SOC and PT (sorted by descending frequency by SOC and PT)
- TEAEs by treatment, SOC and PT Reported by > 5% of subjects in any treatment group
- Related TEAE by treatment, SOC and PT
- Serious TEAEs by treatment, SOC and PT (sorted by descending frequency by SOC and PT)
- Serious Related TEAEs by treatment, SOC and PT (sorted by descending frequency by SOC and PT)
- AEs leading to death by treatment, SOC and PT (sorted by descending frequency by SOC and PT)
- TEAEs leading to discontinuation of trial by treatment, SOC and PT (sorted by descending frequency by SOC and PT)
- TEAEs leading to discontinuation of treatment by treatment, SOC and PT (sorted by descending frequency by SOC and PT)
- TEAEs by treatment and PT (sorted by descending frequency of PT)
- Related TEAEs by treatment and PT (sorted by descending frequency of PT)
- Serious TEAEs by treatment and PT (sorted by descending frequency of PT)
- Deaths by treatment

Detailed listings for all AEs, serious TEAEs, AEs leading to the discontinuation of trial, TEAEs leading to the discontinuation of treatment, AEs leading to death and special situation will also be generated.

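### The TEAE window includes the whole day of the first extension dose, so a control subject's reaction to a first lonapegsomatropin injection could be tabulated under the control arm

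*SAP*

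**What the plan says.** SAP 12.12.1 defines a treatment-emergent adverse event in one sentence with two branches. The new-onset branch requires that "it occurred on or after the first dose of investigational product and was not present prior to the first dose". The worsening branch covers events already present at the first dose that become more severe. The end of the window follows the worsening branch and is the earlier of two limits: "through 14 days after the last dose of treatment on the main period or the date of first dose on the extension period whichever occurs".

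Five other provisions bear on how that limit works:

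- **Extension treatment.** Protocol 5.5: "During the extension trial, all subjects will receive lonapegsomatropin".
- **Arm attribution.** SAP 10.5 places each subject in the safety tables under a single treatment, the one received more of.
- **Collection period.** Footnote c of the Schedule of Events: "The AE collection period begins with signing of ICF and ends at Visit 7 if the subject continues into extension". The SAP repeats this footnote under its Table 1.
- **Onset detail.** Protocol 12.3.2 asks whether onset came before or after dosing only for Day 1 of the main trial. SAP 11.2.3 keeps an event with a date but no time as treatment-emergent unless its day precedes first treatment or follows the end of the study.
- **Visit mapping.** SAP Table 2 closes the Visit 7 window at Day 316 or "first dose date in the TCH-306 EXT which ever is earlier", with that date included.

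**The concern.** The window closes on a day, not at the injection. On that day a placebo or daily-somatropin subject receives lonapegsomatropin, for a naive subject's first time in this programme. A reaction that begins an hour later satisfies the main-trial definition, yet the subject remains in the control arm for the tables. Nothing in the onset data or the missing-time rule would separate it from an event that began that morning before the injection.

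The events most likely to start on an injection day are also the ones of most interest. SAP 12.12.2 counts injection site reactions separately. Hypersensitivity is the important identified risk named in protocol 12.1.4: "There have been reports of hypersensitivity and/or anaphylaxis in clinical trials and the post-marketing setting". Charging such an event to a comparator would dilute the safety contrast for the event types where that contrast is most informative.

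**Working it through.** The plan gives no figure on this point, and the sample-size calculation does not enter. The check is of dates and rules, followed by a scale.

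**1. Is the extension date the operative limit?** It is if it comes sooner than 14 days after the last main-period dose.

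- Weekly arms (protocol 10.2.2.1): Visit 7 is 96–120 h after the last dose, ±3 h, so 93/24 = 3.9 to 123/24 = 5.1 days. If the post-visit DXA week is used in full, add 7: 10.9 to 12.1 days.
- Daily arm (protocol 10.2.2.2): Visit 7 "will be conducted the day after the 26th week (or 27th week) of fixed dosing is completed", so about 1 day, or about 8 with the DXA week.

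All are under 14. In the weekly arms the extension date is the operative limit if dosing starts within about 14 − 5.1 = 8.9 days of Visit 7. The documents do not give the extension start date, but a start at or soon after Visit 7 falls inside this.

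**2. Does a same-day event after the injection qualify?** There are two readings of the sentence.

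- The limit binds both branches: the date is included, so the event qualifies.
- The limit binds only the worsening branch: a new-onset event has no stated end limit, so it qualifies too.

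**3. Which arm receives it?** After 38 weeks of control treatment and one extension dose, SAP 10.5 keeps the subject in the control arm.

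**4. Can it reach the TCH-306 data?** Footnote c ends collection at Visit 7 for subjects who continue. The event is therefore tabulated only if (a) the injection is on the Visit 7 day and the event is entered in TCH-306, or (b) extension events are merged in. Neither is stated. SAP 11.3 accepts DXA assessments dated on the first extension-dose day, so the SAP allows the two to coincide. That rule assigns assessments to visits, not adverse events, and is only indirect support.

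**5. Scale.** One subject is 1/80 = 1.25 percentage points at the planned arm size. If the roughly 282 subjects in SAP section 2 are split equally, 282/3 = 94 and one subject is 1/94 = 1.06 points. The two control arms then hold 282 × 2/3 = 188.

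Expected misattributed events = 188 × rollover × q × same-day event rate, where q is the fraction whose injection-day events are recorded in TCH-306. No document gives these three inputs. Assuming rollover of 80–95% and a same-day rate of 0.5–3%:

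| q | Low | High |
|---|---|---|
| 0 | 0 | 0 |
| 1 | 188 × 0.80 × 0.005 = 0.8 | 188 × 0.95 × 0.03 = 5.4 |

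**6. Direction.** The change in the risk difference (lonapegsomatropin minus control) is the share of newly counted subjects in the lonapegsomatropin arm minus the share in the control arm. One new subject in each arm of 94 gives 1/94 − 1/94 = 0. One in the control arm only gives −1.06 points.

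**The case against.** The strongest reply is that the definition can classify only what the trial collects. Collection stops at Visit 7 for subjects who roll over, and the extension is a separate trial with its own consent (protocol 10.1). In the weekly arms the rhythm also points away from same-day dosing. At Visits 2 to 4, timed like Visit 7, the next injection comes 2–3 days later (Schedule of Events, footnote m). If that rhythm continues into the extension, the first extension dose falls after collection has ended. This stands as a limit on the consequence. It does not repair the rule: footnote m does not cover Visit 7, footnote c does not separate before from after on the Visit 7 day, and a window running to the extension-dose date disagrees with a collection period that ends at Visit 7.

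A reader might infer that these events will be counted against control and that the bias always favours lonapegsomatropin. The documents do not support that. They place no extension injection on the Visit 7 day and describe no merging of data. The extra day is added to all three arms, so equal rates offset in the risk difference. Net dilution needs a higher reaction rate at first exposure, or lonapegsomatropin subjects already counted for the same event. The second is plausible because protocol 14.4.4 counts a subject once per event, but neither can be quantified here.

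It is also fair to say that safety reporting is descriptive, all adverse events are listed, and efficacy is untouched.

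**Conclusion.** The defect in the wording is established: the window includes a day on which control subjects receive the test drug, no other rule separates events before and after that injection, and the limit may not bind new-onset events at all. The misattribution is conditional. It requires the first extension dose to fall on the Visit 7 day, or extension events to be merged into the TCH-306 data.

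The size cannot be derived from the documents. It is near zero if the extension dose always follows Visit 7 and its events are held only in the extension database. Under the assumed rates above, with every such event recorded, it is about 1 to 5 events across both control arms. Each is about 1.1 points of an arm of 94, or 1.25 of an arm of 80. That could matter for a rare event such as hypersensitivity and little for common ones. The correction is worth making because it removes a possible misattribution from the safety tables at almost no cost.

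**What to change.** In SAP 12.12.1:

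1. State that both branches, new onset and worsening, end at the earlier of 14 days after the last main-period dose and immediately before the first extension dose.
2. Assign adverse events known to start after that injection to TCH-306 EXT. Record onset relative to the first extension dose, as is already done for Day 1.
3. Keep same-day events whose order relative to the injection is unknown under the worst-case rule of 11.2.3, but flag them and show counts with and without them. Moving them all to the extension would contradict that rule and could label genuine control-period events as lonapegsomatropin events.
4. Apply the same limit to the injection site reaction counts in 12.12.2.
5. Reconcile the window with footnote c, and state whether extension adverse event records enter the TCH-306 dataset.

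The cost is a few sentences in the SAP, one programming condition and a small flagged listing. Where sites have not recorded the order of onset on that day, the flagged group remains unresolved, but its size will be visible.

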12.12.2. Injection Site Reactions

The number and percentage of subjects will be presented for injection site reactions and injection site reactions resulting in discontinuation.

12.12.3. Other Adverse Events to Monitor

12.12.3.1. Clinical Laboratory Parameters

Descriptive summaries of actual (absolute) values and changes from baseline values if applicable will be presented for the following by treatment and visit:

- Chemistry: sodium, potassium, calcium, chloride, total bilirubin, alkaline phosphatase, lactate dehydrogenase (LDH), aspartate aminotransferase (AST), alanine aminotransferase (ALT), gamma glutamyl transferase (GGT), albumin, total proteins, creatinine (also eGFR calculation per MDRD equation), urea-nitrogen, uric acid, ferritin, and transferrin
- Hematology: hemoglobin, erythrocyte count, hematocrit, mean corpuscular hemoglobin (MCH), mean corpuscular volume (MCV), mean corpuscular hemoglobin concentration (MCHC), leukocytes, differential blood count of leukocytes, platelet count
- Glucose Metabolism: fasting insulin, fasting glucose, HbA1c
- Lipid Metabolism (fasting): total cholesterol, triglycerides, HDL, LDL, Lp(a) lipoprotein, free fatty acids, VLDL
- Thyroid and adrenal status: TSH, fT4, fT3, morning (06:00-10:00AM) cortisol
- Testosterone (males only)

Laboratory values will be displayed in the data listings and those that are outside the normal range will be flagged, along with corresponding normal ranges.

Data listings of laboratory will also be provided, displaying details of each laboratory test for central and local laboratories separately.

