9.6.2. Dose Reductions and Possible Stopping

The investigator may stop or reduce the dose of study drug for an individual subject as per the dosing algorithms showed in [Figure 3](#) and [Figure 4](#), as well as at any time during the trial for the following reasons:

- HbA1c levels:
 - Subjects without diabetes diagnosis at trial start: In case the HbA1c level is $>6.5\%$ and / or has an absolute increase of 0.8% from the prior visit HbA1c: Confirmation of HbA1c level is required. Once confirmed, the study drug dose (lonapegsomatropin/placebo or daily somatropin product) may be decreased to the next lower dose level (see [Table 3](#) and [Table 4](#)) or a diet / nutritional counseling and / or diabetes medication may be added per investigator judgement. If appropriate follow-up monitoring shows progressively worsening glucose intolerance, additional lonapegsomatropin dose adjustments may be appropriate
 - Subjects with diabetes diagnosis at trial start: additional diabetes medication may be added as considered appropriate by the investigator
- Severe hGH-related AEs

Please notify the Medical Monitor as soon as possible in the presence of the following symptoms and laboratory abnormalities:

- Severe hGH-related AEs at any time during the trial
- Evidence of hypersensitivity to the study drug

For subjects who discontinue the study drug for reasons related to safety, unblinding of the treatment assignment for the subject may occur if deemed necessary by the Sponsor to assess a potential safety signal or by the investigator to provide adequate medical care to the subject.

Refer to Section [7.3](#) for termination rules.

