Investigators should use correct medical terminology/concepts when reporting AEs or SAEs. Avoid colloquialisms and abbreviation (e.g., hypertension for elevated blood pressure that persists and requires chronic treatment and follow-up, or increased blood pressure for elevated blood pressure that occurs for a limited time and does not persist or require ongoing treatment).

AEs will be documented at the maximum intensity experienced. If a previously recorded and closed AE or condition recorded as part of medical history increases in severity or frequency, it will be recorded as a new AE.

All AEs will be considered ongoing until they have completely resolved or are deemed stable or commensurate with ongoing disease processes by the investigator. At study completion or the Early Termination Visit, all AEs should have a statement regarding resolution, see also Section 10.2.4 and Section 10.2.5.

An accidental overdose is not an AE if there are no signs or symptoms. Any undesirable medical occurrence resulting from an accidental overdose is an AE and should be recorded and reported on the appropriate eCRF. Regardless of classification as an AE or not, *all* overdoses should be documented, and the subject(s) monitored. Since accidental overdoses with the study drug could have serious clinical consequences and/or represent a compliance issue, they should be reported to the Medical Monitor immediately and evaluated by the Sponsor. See Section 12.1.3.

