12.3.3. Specific Instructions for Recording Adverse Events

Abnormal Laboratory Values

Not every laboratory abnormality qualifies as an AE. A laboratory test result must be reported as an AE if it meets any of the following criteria:

- Is accompanied by clinical symptoms

- Results in a change in study treatment (e.g., dosage modification or titration, treatment interruption, or treatment discontinuation) *Note:* Increased IGF-1 levels (blinded to investigators in this study) requiring study drug dose decrease (ie, IGF-1 SDS > 2.0) will not be considered as AE. However, occurrence of clinically significant symptoms/conditions associated with increased IGF-1 levels will be considered as AE.
- Results in a medical intervention (e.g., potassium supplementation for hypokalemia) or a change in concomitant therapy
- Is clinically significant in the investigator's judgment

It is the investigator's responsibility to review all available laboratory findings. Medical and scientific judgment should be exercised in deciding whether an isolated laboratory abnormality should be classified as an AE.

If a clinically significant laboratory abnormality is a sign of a disease or syndrome (e.g., alkaline phosphatase and bilirubin 5 × ULN associated with cholestasis), only the diagnosis (i.e., cholestasis) should be recorded on the Adverse Event eCRF.

If a clinically significant laboratory abnormality is not a sign of a disease or syndrome, the abnormality itself should be recorded on the Adverse Event eCRF, along with a descriptor indicating whether the test result is above or below the normal range (e.g., "elevated potassium," as opposed to "abnormal potassium"). If the laboratory abnormality can be characterized by a precise clinical term per standard definitions, the clinical term should be recorded as the AE.

Observations of the same clinically significant laboratory abnormality from visit to visit should only be recorded once on the Adverse Event eCRF.

Abnormal Vital Sign Values

Not every vital sign abnormality qualifies as an AE. A vital sign result must be reported as an AE if it meets any of the following criteria:

- Is accompanied by clinical symptoms
- Results in a change in study treatment (e.g., dosage modification, treatment interruption, or treatment discontinuation)
- Results in a medical intervention or a change in concomitant therapy
- Is clinically significant in the investigator's judgment.

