- Hospitalization or prolonged hospitalization for diagnostic or elective surgical procedures for pre-existing conditions
- Hospitalization or prolonged hospitalization required to allow efficacy measurement for the study
- Hospitalization or prolonged hospitalization for scheduled therapy of the target disease of the study.

Pre-existing Medical Conditions

A pre-existing medical condition is one that is present at the start of the study. Such conditions should be reported as medical and prior procedures. A pre-existing medical condition should be re-assessed throughout the trial and reported as an AE or SAE only if the frequency, severity, or character of the condition worsens during the study. When reporting such events, it is important to convey the concept that the preexisting condition has changed by including applicable descriptors (e.g., worsening type 2 diabetes mellitus).

Pregnancy

If a female subject becomes pregnant while receiving the study drug or within 2 weeks after the last dose of study drug, or if the female partner of a male study subject becomes pregnant while the study subject is receiving the study drug, a Pregnancy report form should be completed and expeditiously submitted to Sponsor. Follow-up to obtain the outcome of the pregnancy should also occur and the outcome reported to Sponsor. DXA scans cannot be performed on subjects who are pregnant or suspected to be pregnant.

Abortion, whether accidental, therapeutic, or spontaneous, should always be classified as serious, and expeditiously reported as an SAE. Similarly, any congenital anomaly/birth defect in a child born to a female subject exposed to the study drug should be expeditiously reported as an SAE.

Product Complaints

A Product Complaint is defined as any written or oral information received from a complainant that alleges deficiencies related to identity, quality, safety, strength, purity, reliability, durability, effectiveness, or performance of a product after it has been released and distributed to the commercial market or clinical trial.

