12. STATISTICAL METHODS OF ANALYSES

12.1. GENERAL PRINCIPLES

In general, summaries will be performed descriptively by treatment group. Continuous, quantitative (absolute values at each timepoint and change from baseline if applicable) variable summaries will include the number of subjects (N) with non-missing values, mean, standard deviation (SD), standard error (SE) of the mean, median, minimum, and maximum values.

Categorical, qualitative variable summaries will include the frequency and percentage of subjects in the particular category. In general, the denominator for the percentage calculation will be based upon the total number of subjects in the trial population for the cohorts.

All statistical tests will be two-sided and tested at statistical significant level of 0.05. P-values will be rounded and displayed in three decimals. If a p-value is less than 0.0001, it will be shown in tables as <0.0001. Confidence intervals will be 2-sided 95% confidence intervals, unless stated otherwise.

Unless otherwise specified, all summaries including by-visit summaries will be analyzed for the treatment period (Week 1 to Week 38).

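### SAP 12.12.3.1 plans no count by arm of subjects reaching diabetic-range HbA1c or glucose, or with a large cumulative HbA1c rise, when no AE is recorded; SAP 12.8 does not separate new or increased glucose-lowering drugs from baseline use

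*SAP*

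**What the plan says.** **Laboratory data.** For the glucose-metabolism panel, as for all laboratory parameters, SAP 12.12.3.1 states: "Descriptive summaries of actual (absolute) values and changes from baseline values if applicable will be presented for the following by treatment and visit". SAP 12.1 gives the content of a continuous summary as the number of subjects plus "mean, standard deviation (SD), standard error (SE) of the mean, median, minimum, and maximum values". Values outside the normal range are flagged in listings. SAP 11.3 keeps one value per visit window, the one nearest the target day.

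**Adverse events.** SAP 12.12.1 tabulates "TEAEs by treatment, SOC and PT (sorted by descending frequency by SOC and PT"). Three protocol rules feed these tables:
- Under 12.3.3, a laboratory result must be reported as an AE if it is symptomatic, changes study treatment, is judged clinically significant by the investigator, or "Results in a medical intervention (e.g., potassium supplementation for hypokalemia) or a change in concomitant therapy".
- Under 12.3.2, if a "condition recorded as part of medical history increases in severity or frequency, it will be recorded as a new AE".
- For pre-existing conditions, 12.3.3 asks that the change be conveyed "by including applicable descriptors (e.g., worsening type 2 diabetes mellitus").

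Section 12.3.2 exempts routine titration of chronic concomitant drugs from AE reporting.

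**Dose-action rule.** Protocol 9.6.2 acts, in subjects without diabetes at trial start, when HbA1c exceeds 6.5% and/or "has an absolute increase of 0.8% from the prior visit HbA1c: Confirmation of HbA1c level is required". After confirmation, the study dose may be lowered, or counselling or diabetes medication may be added. For the others: "Subjects with diabetes diagnosis at trial start: additional diabetes medication may be added as considered appropriate by the investigator".

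**Medication.** SAP 12.8 counts each subject once per drug or class, by arm. Its definition of concomitant includes baseline drugs that continue after first dose.

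**The concern.** Glycaemic worsening is a matter of individual subjects crossing a threshold, and an arm's mean at a visit describes it poorly. Protocol 13 names glucose metabolism among the laboratory findings for particular sponsor attention, and safety is a secondary objective. Yet the planned laboratory tables do not say how many subjects without diabetes reached diabetic values, or how many had a large rise. By-visit means can also be pulled down by the dose cuts and added drugs that Protocol 9.6.2 permits.

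AE tables give counts, but an asymptomatic value that changes no treatment becomes an AE only on the investigator's judgement. In the daily somatropin arm that judgement is made knowing the treatment (Protocol 7.1.2.1). Threshold counts from laboratory values do not depend on it.

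**Working it through.** The plan gives no figure of its own on this point. The check sets the provisions side by side and then works through the 9.6.2 trigger.

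**1. What is counted by arm, and what is not**

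| Event | Where it is counted |
|---|---|
| Drug started, or study dose cut, because of a laboratory result | TEAE tables (Protocol 12.3.3, SAP 12.12.1); dose cuts also in SAP 12.5.3, under AE or Other, with no HbA1c category |
| Recorded worsening of known diabetes | TEAE tables (Protocol 12.3.2 and 12.3.3) |
| Any use of a glucose-lowering drug | SAP 12.8, with baseline use and new starts mixed |
| Diabetic-range value or large rise, no AE recorded | Listings only |
| Dose increase treated as routine titration | Not tabulated |

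Protocol 9.9.2.1 makes optimising the metformin or DPP-4 inhibitor dose the first response to rising glucose. Prompted by a laboratory result, that increase is an AE under 12.3.3. Regarded as routine titration, it is exempt under 12.3.2.

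**2. What the 9.6.2 trigger misses**

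Inputs: the trigger is above 6.5%, or +0.8 points from the prior visit. The trial's diabetes definition (exclusion criterion 2b) is HbA1c of at least 6.5% and/or fasting glucose of at least 126 mg/dL (or a two-hour value after an oral glucose load). The Schedule of Events gives five post-baseline safety-laboratory visits (Visits 2, 4, 5, 6 and 7). With HbA1c to one decimal, each step can be at most 0.7 without triggering.

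Largest untriggered rise from baseline b = min(6.5 − b, 5 × 0.7):

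| Baseline HbA1c (%) | 5.0 | 5.3 | 5.5 | 5.7 | 5.8 |
|---|---|---|---|---|---|
| Largest rise (points) | 1.5 | 1.2 | 1.0 | 0.8 | 0.7 |

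- 5.4 → 5.9 → 6.4: rise 1.0, largest step 0.5, trigger not met.
- 5.5 → 6.0 → 6.5: rise 1.0, trigger not met, yet 6.5% meets the diabetes definition.
- 5.8 → 6.2 → 6.6: rise 0.8, trigger met because 6.6 exceeds 6.5.

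A rise of 0.8 or more can go untriggered only from a baseline of 5.7% or lower (6.5 − 0.8 = 5.7). Fasting glucose has no numeric trigger, and subjects with diabetes at trial start have no numeric HbA1c trigger.

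**3. What the planned summaries would show (illustration)**

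The numbers affected, the SDs and normality are assumptions; 80 per arm is from the protocol.

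- Mean shift when k subjects rise by 0.8 at one visit = (k/80) × 0.8: 0.04 for k = 4 and 0.08 for k = 8. If the eight peaks are spread evenly over four visits and then corrected, each mean shifts by (2/80) × 0.8 = 0.02.
- 95% half-width for the difference between two arms = 1.96 × SD × √(2/80): 0.06 for an SD of change of 0.2 and 0.15 for 0.5.
- Simulated arms of 80 (20,000 per setting): the median maximum change with 0, 4 and 8 affected subjects is 0.95, 1.23 and 1.36 at SD 0.4, and 0.48, 1.00 and 1.08 at SD 0.2. An arm with four affected shows a maximum at least as large as an arm with eight in 35% of pairs (33% at SD 0.2).

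The maximum signals that a large rise occurred. It does not say how many subjects had one.

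**4. False positives in a threshold count**

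Assume a stable true HbA1c of 6.2%, within-subject SD 0.15 and five independent values. A single value reaches 6.5% with probability p = P(Z ≥ 0.3/0.15) = 0.0228. Any of five: 1 − (1 − 0.0228)^5 = 10.9%. Two consecutive values: at most 4 × p² = 0.21%. For SD 0.10 to 0.20 the ranges are 0.7% to 29% for any value, and below 0.01% to 1.7% for confirmed values.

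**The case against.** The strongest reply is that the AE rules already catch most of this. A missed case needs a diabetic-range value or a large rise with no symptoms, no change in study drug or other therapy, and an investigator who judges it not significant. Above 6.5%, confirmation is mandatory in subjects without diabetes. The HbA1c example that reaches the definition without triggering needs a value of exactly 6.5%. The documents give no frequency for any of this. Protocol 14.4.4 promises descriptive safety reporting by visit, and the SAP delivers it with subject-level listings, so the counts could be produced later.

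Most of that stands, and it is why the point is narrow. It does not remove the gap. Each response to a confirmed value is optional, glucose has no numeric trigger, and a listing leaves the reader to do the counting.

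A reader might infer more: that new glucose-lowering treatment, or study-dose cuts for rising HbA1c, are counted nowhere. The documents do not support this. Protocol 12.3.3 makes both reportable AEs when a laboratory result prompts them, SAP 12.8 counts users by drug and class, and SAP 12.5.3 counts dose adjustments by reason. What remains is that new starts are not separated from baseline use, and increases treated as routine titration are not tabulated.

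The 0.8-point rise from baseline is also a borrowed cut-off: the protocol uses 0.8 only against the prior visit.

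**Conclusion.** The concern holds in a narrow form. In the visible SAP, no table counts by arm the subjects without diabetes who reach diabetic-range HbA1c or fasting glucose, or the subjects with a large cumulative HbA1c rise, when no AE is recorded. The untriggered rise can be as large as 1.5 points from a baseline of 5.0%. New or increased glucose-lowering therapy cannot be read directly from the medication tables.

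Severity is low: safety reporting only, with no effect on the efficacy analysis or the error rate. The trigger arithmetic comes from the documents, with HbA1c taken to one decimal. The dilution, maximum-change and false-positive figures rest on assumed inputs and say nothing about how often this will happen in the trial. The tertiary and exploratory sections are redacted and part of the appendix is not available, so a glycaemic table there cannot be excluded, although SAP 12.12, where safety analyses belong, is visible.

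**What to change.** Keep the existing summaries and add descriptive n (%) tables by arm and baseline diabetes status (already a subgroup variable in SAP Table 3). Use all post-baseline values, scheduled and unscheduled, with the central laboratory as main source.

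1. Subjects without diabetes, and below both thresholds, at baseline: any post-baseline HbA1c of at least 6.5% or fasting glucose of at least 126 mg/dL. Add a separate row for confirmed values, where a repeat sample (local results accepted) or the next scheduled value also meets the threshold.
2. Subjects with an HbA1c rise from baseline of at least 0.8 points, labelled as a descriptive cut-off.
3. In the SAP 12.8 tables, a separate row for glucose-lowering drugs newly started, or increased in dose, after first dose.

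Denominators are subjects with a post-baseline value for items 1 and 2, and the Safety Analysis Set for item 3. No formal test.

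The cost is one or two tables and a derivation of dose changes that SAP 12.8 does not now contain. The data are already collected: Protocol 9.9.2 requires changes in concomitant medication, with dose, in the eCRF. The drawback is some single-value false positives in every arm, which the confirmed row largely removes (about 10.9% down to about 0.2% under the assumptions above).
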